8.10. Pharmacodynamic (PD) Analyses

Samples for FGF19 are collected via intensive sampling according to the schedule of activities in Section 1.3 of the protocol. Samples for 7 α C4 are collected via trough and intensive sampling according to the schedule of activities in Section 1.3 of the protocol.

8.10.1. Below the Quantification Level (BLQ) Values

Plasma concentrations for 7 α C4, FGF19, [REDACTED] parameters that are BLQ will be set to $\frac{1}{2} \times$ BLQ.

8.10.2. Concentration-Time Data

Individual plasma concentration data for [REDACTED] 7 α C4 will be listed for all patients (trough samples) and separately for PK/PD substudy patients only (7 α C4 and FGF19 only, intensive samples). Concentrations will be summarized by nominal sampling time point and treatment group with descriptive statistics (number of non-missing observations, arithmetic mean, SD, median, minimum, maximum, geometric mean and geometric coefficient of variation [CV%]). The number of values BLQ will be presented for all patients and separately for PK/PD substudy patients (7 α C4 and FGF19 only, intensive samples).

The following rules will be applied in the presentation of plasma concentration data if there are values that are BLQ or if there are missing values (e.g., no result [NR]) in a plasma concentration data series to be summarized.

- For the calculation of summary statistics, BLQ values will be set to $\frac{1}{2} \times$ BLQ.
- Where there is NR, these will be set to missing.
- If there are less than three values in the data series, only the minimum, maximum and number of observations will be presented. The other summary statistics will be denoted as not calculated (NC). BLQ is considered a value.
- If all the values are BLQ, then the arithmetic mean, arithmetic SD, median, minimum and maximum will be presented as $\frac{1}{2} \times$ BLQ, and the geometric mean and geometric CV% will be denoted as NC.

Individual patient and geometric mean concentration-time profiles, for each TERN-101 dose, will be presented graphically on linear and logarithmic concentration scales for PK/PD substudy patients for Day 1 and Week 12.

Concentration data in listings will be presented to the same number of significant figures as provided by the analytical laboratory. Descriptive statistics will be displayed according to the rules outlined in [Section 3.2](#).

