2.2.3. Clinical Trials of TERN-101

TERN-101 has been administered to healthy human subjects in 4 completed Phase 1 clinical studies as described below. As of 14 January 2020, a total of 119 human subjects have received at least 1 dose of TERN-101 in these 4 studies combined (Table 2).

Table 2 List of Completed TERN-101 Clinical Studies

Study Number and Number of Subjects	Study Title
[REDACTED]	[REDACTED]
[REDACTED]	[REDACTED]
TERN101-US-A101 (N = 36)	A Single Center, Randomized, Double-blind, Placebo-controlled, Parallel-group, Multiple Dose, Phase I Clinical Trial to Evaluate the Safety, Tolerability, Pharmacokinetics, and Pharmacodynamics of Orally-Administered TERN-101 in Healthy Subjects
TERN101-US-A104 (N = 34)	An Adaptive, Multi-Part Phase I Study in Healthy Subjects to Compare the Pharmacokinetics of Tern-101 Tablets and Capsules, and to Investigate the Effects of Food and Co-administered Medications on the Pharmacokinetics of Orally Administered TERN-101 Tablets

[REDACTED]

In the fourth study, TERN101-US-A104 (N = 34), TERN-101 25 mg capsule was administered as a single oral dose, and TERN-101 tablets were administered as single oral doses of 5 and 25 mg. TERN-101 tablet PK was dose linear in the range of 5 mg to 25 mg for the tablet formulation. Following single doses of TERN-101 tablets administered in the fasted state, area under the concentration-time curve (AUC)_{0-inf} was 453 (31.3) ng*hr/mL, 2720 (25.2) ng*hr/mL, and 689 (45.0) ng*hr/mL for TERN-101 5-mg tablet, 25-mg tablet, and 25-mg capsule, respectively. Maximal plasma concentrations on average were reached at 0.75 hours postdose for

TERN-101 5-mg tablet and at 1.52 hours for TERN-101 25-mg tablet. Transient increases in FGF-19 concentrations and dose-dependent decreases in 7- α -C4 concentrations were observed after single doses of TERN-101 tablets. Administration of TERN-101 (5 mg) tablet with food delayed the time of maximal plasma concentrations (from ~1 hour fasted to ~4 hours fed) but did not result in significant differences in exposure as assessed by AUC. [REDACTED]

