2.2. Study Design

This study is a randomized, double-blind, placebo-controlled, parallel-group, Phase 2a study to evaluate the safety, tolerability, efficacy, and PK of various doses of TERN-101 in non-cirrhotic presumed non-alcoholic steatohepatitis (NASH) patients. TERN-101 is a highly selective and potent small molecule agonist of farnesoid X receptor (FXR) in development for the treatment of patients with NASH, a serious and advanced form of non-alcoholic fatty liver disease (NAFLD). The study aims to characterize the effects of varying doses of TERN-101 in a NAFLD patient

population with presumed NASH. Currently, there are no approved therapies for the treatment of NASH.

Figure 1 describes the overall study design. The total study duration will be approximately 24 weeks, consisting of an 8-week Screening Period, a 12-week Treatment Period and a 4-week Follow-up Period.

Figure 1: Overall Study Design

Abbreviations: MRI-PDFF = magnetic resonance imaging proton density fat fraction; PK/PD = pharmacokinetics/pharmacodynamics; QD = once a day

Of the approximately 96 patients randomized, 24 patients will take part in an intensive PK and pharmacodynamic (PD) collection after the first dose and after the last dose of study drug. This includes 6 patients at each TERN-101 dose level, and 6 patients in the placebo group. Patients who are not participating in the PK/PD sub-study will have trough PK/PD sampling only.

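### When every PD value is BLQ, SAP 8.10.2 prints an SD of half the limit (it should be 0 or NC) and withholds a geometric mean that its own substitution rule makes calculable.

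*SAP*

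**What the plan says.** SAP 8.10.1 sets BLQ values of the PD analytes to half of BLQ, which I read as half the quantification limit. SAP 8.10.2 repeats this for the tables: "For the calculation of summary statistics, BLQ values will be set to" half of BLQ.

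A later bullet in 8.10.2 covers the case where nothing is quantifiable: "If all the values are BLQ, then the arithmetic mean, arithmetic SD, median, minimum and maximum will be presented as" half of BLQ, "and the geometric mean and geometric CV% will be denoted as NC".

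The paragraph after the bullets specifies the figures: "Individual patient and geometric mean concentration-time profiles, for each TERN-101 dose, will be presented graphically on linear and logarithmic concentration scales", for the PK/PD sub-study patients on Day 1 and at Week 12. SAP 2.2 gives the size of that sub-study: "This includes 6 patients at each TERN-101 dose level, and 6 patients in the placebo group".

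SAP 8.10.2 also plans a separate BLQ count: "The number of values BLQ will be presented for all patients", and again for the sub-study patients.

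On the direction of effect, Protocol 2.2.3 reports from Phase 1 that "dose-dependent decreases in 7- α -C4 concentrations were observed after single doses of TERN-101 tablets".

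**The concern.** The all-BLQ bullet does not agree with the substitution rule a few lines above it. Once each value has been replaced by the same number, the spread is fixed at zero and the geometric mean is fixed at that number. The bullet prints a non-zero spread and declines to give the geometric mean.

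For a drug concentration, a wholly BLQ time point means little drug and is of small interest. 7αC4 is different because TERN-101 lowers it, so low values are the signal. FXR target engagement is a stated exploratory objective. If a whole dose group fell below the limit at a time point, the group curve would have a gap where the measured values are lowest. The argument does not carry over to FGF19, which Protocol 2.2.3 reports as rising transiently on drug.

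**Working it through.** **Inputs.** L is the quantification limit (its value is not given). Each BLQ value becomes L/2 (SAP 8.10.1 and 8.10.2). There are n = 6 sub-study patients per dose (SAP 2.2). The plotted summary is the geometric mean (SAP 8.10.2).

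**1. The plan's arithmetic figures when all six values are BLQ.** Every x = L/2.
- Mean = 6 × (L/2) / 6 = L/2. Median, minimum and maximum are also L/2. These four agree with the bullet.
- SD = √[Σ(x − mean)² / (n − 1)] = √(0/5) = 0. The bullet prints L/2, which is not reproduced. Dividing by n instead of n − 1 also gives 0.
- Printing SD = L/2 beside mean = L/2 implies CV = (L/2)/(L/2) = 100%, in a row where minimum equals maximum.
- Example with L = 2: mean, median, minimum and maximum are 1 and the SD is 0; the bullet would print an SD of 1.

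**2. The geometric figures.**
- Geometric mean = exp[(1/6) × 6 × ln(L/2)] = L/2.
- Geometric CV = √(exp(s²) − 1), where s is the SD of the logs. Here s = 0, so it is 0%.

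The geometric mean can therefore be calculated. The arithmetic would force NC only if BLQ values were set to 0, and for the PD analytes they are not. The small-series rule does not explain the NC either: it applies below three values, and 8.10.2 counts a BLQ result as a value.

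**3. The step between 5 of 6 and 6 of 6.** With five values at L/2 and the sixth at m × L, the geometric mean is L × (0.5⁵ × m)^(1/6).
- m = 1: 0.56 L
- m = 1.5: 0.60 L
- m = 2: 0.63 L

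All of these would be plotted. When the sixth patient also falls below the limit, the consistent value is 0.50 L, but the rule gives NC and there is nothing to plot.

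**4. How often this could happen.** The documents give neither L nor a BLQ rate. Assume that each patient at a dose is BLQ at a given time point with probability p, independently of the others. The chance that all six are BLQ is then p⁶.

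| Assumed p | p⁶ |
|---|---|
| 0.25 | 0.02% |
| 0.50 | 1.6% |
| 0.75 | 17.8% |
| 0.90 | 53.1% |
| 0.95 | 73.5% |

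The range runs from negligible to likely, and nothing in the documents narrows it.

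**The case against.** The strongest case on the other side accepts the SD arithmetic and disputes the consequences.

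- **The trigger may never occur.** Protocol 2.2.3 reports decreases in 7αC4. It does not say that any value fell below quantification. This stands.
- **The cell would not look like missing data.** For an all-BLQ cell the table still gives the number of observations, the BLQ count, and the mean, median, minimum and maximum at half the limit. Individual values are listed and individual profiles are plotted. A careful reader would see six observations, six of them BLQ. This stands, and it limits how far the printed SD can mislead.
- **The comparative analysis is untouched.** SAP 8.10.3 fits an ANCOVA to change and percent change from baseline, with a Wilcoxon/Hodges-Lehmann alternative, and the substituted values stay in. 7αC4 troughs are also taken from all patients, about 24 per arm, so a trough cell would need about 24 of 24 BLQ to trigger the rule. This stands.
- **Declining to report a geometric mean built only from imputed constants is a defensible convention.** This stands in part. The SAP does report the arithmetic mean and median of the same constants, so it does not follow that convention consistently. It also names the geometric mean as the plotted summary. The SAP does not say how an NC cell is drawn; that the point would be absent is an inference, though a natural one.

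A reader might infer that the 7αC4 curve will lose its nadir and that dose response in target engagement will be understated. The documents do not support that. No quantification limit or BLQ rate is given, and the dose comparisons in 8.10.3 keep the imputed values. Nor is an all-BLQ cell proof of maximal suppression: it shows only that values lie below the limit, and the size of the fall also depends on baseline.

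**Conclusion.** The rule is wrong as written. The SD instruction gives an incorrect figure every time it is triggered: L/2 where the substituted data give 0 and the true SD cannot be estimated. The NC for the geometric mean is inconsistent with the SAP's own substitution, which gives L/2. Both conclusions follow from the SAP text and need no assumption beyond reading half of BLQ as half the quantification limit.

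The effect on the figure is conditional. If all sub-study patients at a dose are BLQ for 7αC4 at a time point, the geometric-mean profile has no value there, whereas 5 of 6 BLQ would give one. How often that would occur cannot be known from the documents; the p⁶ range above rests on assumed probabilities and independent patients.

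The reach is small: the descriptive table and the geometric-mean figure. Individual profiles, BLQ counts, the arithmetic mean and median, the trough data and the ANCOVA are not affected. This is a minor wording correction that is worth making.

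**What to change.** Reword the one bullet in SAP 8.10.2 for the PD analytes. If all values in a series are BLQ:

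- present the mean, median, minimum, maximum and geometric mean as ½ × LLOQ, flagged 'all BLQ';
- show the SD and geometric CV% as NC;
- plot the geometric-mean point at ½ × LLOQ, with an LLOQ reference line in the figure.

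Writing LLOQ in place of BLQ in the multiplier removes a loose term. The same edit could say which rule takes precedence when fewer than three values are available and all are BLQ.

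The cost is one bullet and small changes to the table and figure shells. SAP Section 1 allows changes to planned analyses without a new SAP version, with significant ones included in the CSR. The downside is that the plotted point then rests wholly on imputed values; the flag and the reference line disclose this.

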8.10.3. Change from Baseline

Descriptive statistics of [REDACTED], 7 α C4, and FGF19 values, change from baseline, and percent change from baseline values will be presented by treatment group for each visit using the PD Analysis Set. Analyses of 7 α C4 will include both trough and intensive samples.

Analyses of change and percent change from baseline will be carried out using an ANCOVA model at each post-baseline visit with change (percent change) from baseline as the dependent variable including treatment group as a fixed effect and baseline as a covariate. The primary analysis of change (percent change) will be carried out using available observed data only, without imputation for missing data.

The estimates of LS means, SE, and 90% and 95% CIs will be presented by treatment group. Estimates of the LS mean difference between pooled TERN-101 (All TERN-101) and placebo, and each pairwise comparison between placebo and each active dose of TERN-101, will be presented with the associated standard error of the difference, and 90% and 95% CIs of the difference.

The same ANCOVA model will be used to present the last on treatment value for Week 12, to be labelled as “End of Treatment”. For patients who complete Week 12, the Week 12 value will be used. For patients who do not complete treatment, the last value on treatment will be used.

Figures of LS mean (\pm SE) changes from baseline and percent changes from baseline will be presented over time by treatment group.

The distribution of change (percent change) values will be evaluated visually for normality assumptions. If normality assumptions are violated, i.e. data are not normally distributed, a Wilcoxon Rank Sum Test will be used to compare each TERN-101 dose to placebo, and pooled TERN-101 (All TERN-101) to placebo. The median differences and 90% and 95% CI of the median differences between treatment groups will be constructed using Hodges-Lehmann estimate.

[REDACTED]

[REDACTED]

[REDACTED]

9. SAFETY ANALYSES

Safety analyses will be conducted using the Safety Analysis Set.

No inferential comparison of safety endpoints will be performed, unless otherwise specified.

Study drug administration including missed doses, delays, and overdoses, and study drug dispensing and accountability, calculated durations of exposure, and calculated compliances will be presented in by-patient data listings.

9.2. Adverse Events

Adverse event (AE) verbatim terms on eCRFs will be mapped to preferred terms (PT) and system organ classes (SOC) using MedDRA. AE severity will be categorized using the National Cancer Institute Common Terminology Criteria for Adverse Events (NCI CTCAE, Version 5).

All AEs will be listed, but summaries will be restricted to TEAEs, defined as any AE with a start date on or after the date of first administration of study drug through 30 days after the last administration of study drug or through the Follow-Up Period (Week 16). Related SAEs after Week 16 will be considered TEAEs. If it cannot be determined whether an AE is treatment emergent due to a partial onset date, then it will be counted as such. Methodology for imputation of partial AE start and stop dates is described in [Appendix 2](#). Each summary will be displayed by treatment group.

9.2.1. Overall Summary of Adverse Events

An overall summary of TEAEs will be presented by treatment group. The number and percentage of patients who experience at least one of the following:

- Any TEAE, All CTCAE grades
- Grade 3 or higher TEAE
- Serious TEAE
- TEAE leading to death
- Treatment-related TEAE, All CTCAE grades
- Treatment-related Grade 3 or higher TEAE
- Treatment-related serious TEAE
- TEAE leading to study drug interruption
- TEAE leading to study drug discontinued
- TEAE leading to discontinuation from the study

9.2.2. Patient Incidence of Adverse Events

Summaries will be displayed by SOC and PT, and will be ordered by descending order of all TERN-101 incidence of system organ class and preferred term within each system organ class. Summaries of the following types will be presented:

- Patient incidence of TEAEs by MedDRA SOC and PT. [REDACTED]
- Patient incidence of TEAEs by MedDRA SOC, PT, and highest severity (CTCAE grade). At each level of patient summarization, a patient is classified according to the highest severity if the patient reported 1 or more events. AEs with missing severity (CTCAE grade) will be considered Grade 3 (severe) for this summary.
- Patient incidence of CTCAE Grade 3 or higher TEAEs by MedDRA SOC and PT. At each level of patient summarization, a patient is classified according to the highest severity if the patient reported 1 or more events. AEs with missing severity (CTCAE grade) will be considered Grade 3 (severe) for this summary.
- Patient incidence of treatment-related TEAEs by MedDRA SOC and PT. Related AEs are those with relationships reported as “Definitely Related” or “Possibly Related”. At each level of patient summarization, a patient is classified according to the closest relationship to study drug if the patient reported 1 or more events. AEs with a missing relationship will be considered related for this summary.
- Patient incidence of treatment-related CTCAE Grade 3 or higher TEAEs by MedDRA SOC and PT. At each level of patient summarization, a patient is classified according to the highest severity if the patient reported 1 or more events. AEs with missing severity (CTCAE grade) will be considered Grade 3 (severe) for this summary. AEs with a missing relationship will be considered related for this summary.
- Patient incidence of serious TEAEs by MedDRA SOC and PT.
- Patient incidence of TEAEs leading to study drug discontinued by MedDRA SOC and PT. This is a subset of the AEs where Action Taken with Study Drug is checked as “Study drug discontinued.”

The following listings will be presented by treatment group and patient, include study day event started and the duration of event:

- All adverse events.
- Serious adverse events (subset of the AEs where serious is marked as “Yes”).
- CTCAE Grade 3 or higher adverse events (subset of AEs where severity is marked as CTCAE Grade 3, 4, or 5).
- Related adverse events (subset of the AEs where relationship marked as “Definitely Related” or “Possibly Related”).

- Adverse events leading to study drug interruption (subset of the AEs where Action Taken with Study Drug is checked as “Study drug interrupted”).
- Adverse events leading to study drug discontinued (subset of the AEs where Action Taken with Study Drug is checked as “Study drug discontinued”).
- Adverse events leading to death (subset of the AEs where outcome is indicated as “Fatal” or the CTCAE grade is 5 or seriousness criteria is Death).

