
• The investigator is obligated to assess the relationship between study drug and each occurrence of each AE and/or SAE.• The Investigator (or designee) will make a determination of the relationship of the AE to the study drug using a 4-category system according to the following guidelines:
○ Not Related: The AE is definitely caused by the subject's clinical state or the study procedure/conditions.○ Unlikely Related: The temporal association between the AE and the drug is such that the drug is not likely to have any reasonable association with the AE.○ Possibly Related: The AE follows a reasonable temporal sequence from the time of drug administration but could have been produced by the subject's clinical state or the study procedures/conditions.○ Related: The AE follows a reasonable temporal sequence from administration of the drug, abates upon discontinuation of the drug, follows a known or hypothesized cause effect relationship, and (if appropriate) reappears when the drug is reintroduced.• For each AE and/or SAE, the investigator must document in the medical notes that he/she has reviewed the AE and/or SAE and has provided an assessment of causality.• There may be situations in which an SAE has occurred and the investigator has minimal information to include in the initial report to the Sponsor or designee. However, it is very important that the investigator always make an assessment of causality for every event before the initial transmission of the SAE data to the Sponsor or designee.

• The investigator may change his/her opinion of causality in light of follow-up information and send a SAE follow-up report with the updated causality assessment.• The causality assessment is one of the criteria used when determining regulatory reporting requirements.
Follow-up of AEs and SAEs

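### SAP 9.2.2 defines related AEs with a label, *Definitely Related*, that the protocol's causality scale lacks, and omits that scale's top label, *Related*: wrong as written, probably harmless, and simple to correct

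*SAP*

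**What the plan says.** **Protocol, Appendix 6 (Assessment of Causality).** The investigator rates each AE "using a 4-category system according to the following guidelines". The four categories are *Not Related*, *Unlikely Related*, *Possibly Related* and *Related*. The top one is defined as "Related: The AE follows a reasonable temporal sequence from administration of the drug, abates upon discontinuation of the drug", with further conditions following.

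**SAP 9.2.2, summary of treatment-related TEAEs.** "Related AEs are those with relationships reported as “Definitely Related” or “Possibly Related". The same item adds that "a patient is classified according to the closest relationship to study drug if the patient reported 1 or more events", and that "AEs with a missing relationship will be considered related for this summary".

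**SAP 9.2.2, listings.** The pair of labels appears again: "Related adverse events (subset of the AEs where relationship marked as “Definitely Related” or “Possibly Related".

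**Protocol 9.4.2** commits the sponsor to TEAE summaries by study drug causality and to a summary of TEAEs related to study drug.

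**The concern.** The SAP's rule is written in terms of recorded values, and those values do not match the scale the protocol gives to investigators. *Definitely Related* is not on that scale. Its only use of the word definitely is at the opposite end: "Not Related: The AE is definitely caused by the" patient's own condition or the study procedures. The category with the firmest attribution to drug, *Related*, is absent from the SAP rule.

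This is a safety and tolerability trial, so the related-TEAE table will be read closely. Taken literally together, the two documents produce an odd result. An AE that the investigator attributed firmly to study drug would be left out of the table, while an AE for which nobody recorded an opinion would be counted in it.

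**Working it through.** There is no figure in the plan to reproduce, so the check compares labels, then reach, then the size of one lost patient.

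**1. Labels side by side**

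| Label | On protocol scale (Appendix 6) | In SAP 9.2.2 related rule |
|---|---|---|
| Not Related | yes | no |
| Unlikely Related | yes | no |
| Possibly Related | yes | yes |
| Related | yes (strongest) | no |
| Definitely Related | no | yes |

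Of the SAP's 2 labels, 1 is on the protocol's 4-label scale.

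**2. Does visible text bridge the gap?** The missing-relationship rule does not, because a recorded *Related* is not a missing value. SAP Section 11, where substantial departures from the protocol are to be identified, covers analysis sets and endpoint clarification and does not mention causality. Part of 9.2.2 and the appendix text ahead of Appendix 3 are blacked out, so a mapping could be there. The eCRF code list is not in either document.

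**3. Two readings**

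- *Reading 1:* the eCRF's top option is worded *Definitely Related*. The filter then picks up the top two categories and 0 AEs are lost.
- *Reading 2:* the data carry the protocol's labels and the filter is applied literally. Every AE marked *Related* leaves the listing. A patient leaves the summary if he or she has at least one TEAE marked *Related* and none that is *Possibly Related* or has missing causality.

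**4. Reach.** Relatedness is used in 10 places in SAP 9.2 to 9.2.3:

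- 9.2: 1 (the rule that related SAEs after Week 16 count as TEAEs)
- 9.2.1: 3 rows
- 9.2.2: 3 (two summaries and one listing)
- 9.2.3: 3 pruritus rows

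1 + 3 + 3 + 3 = 10. Two of these state the definition (one summary and the listing in 9.2.2). The other 10 − 2 = 8 do not, and are affected only if they inherit it.

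**5. Size of one lost patient under reading 2.** The planned arms are 24 each, and the three TERN-101 arms pooled give 3 × 24 = 72.

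- One arm: 1/24 = 4.2 percentage points
- Pooled: 1/72 = 1.4 percentage points

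These are per-patient steps, not an estimate of the total effect. The documents give no expected rate of related AEs, and none is assumed here.

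**The case against.** The strongest answer is that *Definitely Related* is simply what the form says. Several points support this.

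- Neighbouring rules in 9.2.2 appear to quote form options, for example "Action Taken with Study Drug is checked as “Study drug interrupted".
- The SAP is dated 19 May 2021, about a year after Protocol Amendment 1 (22 May 2020). It describes some study conduct in the past tense, so its authors probably had the live eCRF in front of them.
- Each document has exactly one category stronger than *Possibly Related*, so the mapping is natural.
- Reading 2 requires a programmer to see AEs coded *Related* and exclude them from a table of related AEs.

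This stands, and it makes reading 1 the likelier one. It does not make the rule correct as written: a filter that quotes literal values should match the data or state its mapping.

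Three further points also stand. Section 11 need list only substantial differences, so its silence fits a mere label variant. Stating a definition once and not repeating it in every bullet is normal drafting, so the 8 places without their own definition are not 8 separate defects. And one might add that, under reading 2, a patient with both a *Related* and a *Possibly Related* event would be kept but classified a category too low. The summary is described as by SOC and PT, with no stated breakdown by relationship, so that effect may never appear.

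A reader might infer more: that the SAP does discard the AEs most firmly attributed to drug, or that the primary safety results are compromised. The documents do not support either. The first rests on a code list they do not show. On the second, the primary endpoints in SAP 2.3.1 are incidence of TEAEs and of treatment-emergent laboratory abnormalities, and neither filters on causality. The one indirect route is the post-Week-16 related-SAE rule in 9.2, and only if it inherits these labels.

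**Conclusion.** The mismatch between the two documents is certain, and the SAP rule is wrong as written. Severity is low because any consequence is conditional.

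Under the likelier reading the effect is zero and only the wording needs aligning. Under the other, AEs marked *Related* drop out of the related-TEAE summary and the related-AE listing, at 4.2 points per lost patient in an arm of 24 or 1.4 points in the pooled 72. That outcome rests on two assumptions: that the data carry the protocol's labels, and that the filter is applied literally. The point sizes also assume the planned arm sizes.

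No event would disappear from reporting. The all-cause TEAE, serious and Grade 3 or higher outputs do not use the filter, nor does the summary of all pruritus TEAEs, and SAP 9.2 lists every AE. Safety is descriptive, so no formal test is at stake.

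**What to change.** Check the eCRF causality code list. Then define related in the SAP as the protocol's top two categories, *Related* or *Possibly Related*, and state the mapping explicitly if the eCRF uses a different label. Use that definition for every treatment-related output in 9.2.1, 9.2.2 and 9.2.3, and for the post-Week-16 related-SAE rule in 9.2. Keep the treatment of missing causality as related in the summaries.

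Cost: one look at the code list, one sentence in the SAP and one cross-reference.
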